All products will be stored according to instructions from the manufacturer, in a dry and cool place at a temperature below 30° C out of direct sunlight. Prior to providing participants with products, the products will be inspected visually for damage. Quality control procedures will be detailed in a study standard operating procedure (SOP).

Outcomes

The outcomes of the study, their definitions, and type of analysis (non-inferiority or superiority) are listed in Table 3. Treatment outcomes will be evaluated through non-inferiority, and post-treatment outcomes will be evaluated through superiority analyses. This is because the intervention products may have the important benefits described above of being lower cost than the standard RUTF, increased potential to be produced locally, and free of aflatoxin, but evidence is needed to confirm they are acceptably similar in treatment outcomes. The composition of these alternative formulations may also improve gut health, possibly reducing the risk of relapse. Thus, post-discharge relapse outcomes are analyzed in superiority analyses.

Table 3. Primary and secondary study outcomes

Outcomes	Definition	Type of analysis
Primary outcomes		
Anthropometric recovery at discharge	WLZ \geq -2 and MUAC \geq 125 mm and absence of bilateral pitting edema for two consecutive visits	Non-inferiority
Relapse to wasting within 3-months post-discharge	A new episode of wasting (defined as WLZ/WHZ $<$ -2 or MUAC $<$ 125 mm or presence of bilateral pitting edema) within the 3-month period following recovery from the index wasting episode, among children who recovered from their index episode	Superiority
Secondary outcomes		
Length of stay (LOS) among recovered children:	The number of days between the day the child is admitted to treatment and the day the child is determined to be recovered and thus discharged from treatment	Non-inferiority
Weight gain	Change in child's weight (gram/kilogram/day) between weight on day of admission to treatment and day of discharge	Non-inferiority
Default from treatment	Child is absent for two consecutive visits, declared a defaulter on the second visit	Non-inferiority
Transfer to inpatient treatment	Referral or admission to hospital for inpatient treatment during the treatment course	Non-inferiority

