Non-response to treatment	Any of the following criteria are met: Absence of weight gain after 5 weeks or at the third visit; weight loss for more than 4 weeks in the program or at the second visit; loss of more than 5% of body weight compared to admission weight at any time; or anthropometric recovery criteria not met after 3 months of follow-up in CMAM	Non-inferiority

Adherence to treatment services	Caregiver attends the recommended schedule of visits and receive RUTF supply	Non-inferiority
Compliance to treatment services	The child receives the recommended dose of the RUTF each day	Non-inferiority
Anthropometry at discharge from treatment	WLZ/WHZ, MUAC, weight, height/length, LAZ/HAZ and WAZ at discharge from treatment	Non-inferiority
Anthropometry at 3-months post-discharge	WLZ/WHZ, MUAC, weight, height/length, LAZ/HAZ and WAZ at 3-months post-discharge	Superiority
Relapse to SAM	A new episode of SAM (WLZ/WHZ < -3 or MUAC < 115 mm or presence of bilateral pitting edema) within the 3-month period following recovery from the index wasting episode	Superiority
Relapse to MAM	A new episode of MAM (WLZ/WHZ < -2 and \geq -3, or MUAC < 125 mm and \geq 115 mm) within the 3-month period following recovery from the index wasting episode	Superiority
Morbidity	Indication of morbidity (acute respiratory infections, diarrhea, fever, or malaria) on health center card	Non-inferiority
Hemoglobin at discharge	Hemoglobin concentration (grams/liter) at discharge	Non-inferiority
Hemoglobin at 3-months post-discharge	Hemoglobin concentration (grams/liter) at 3-months post-discharge	Superiority
Anemia at discharge	For children 6-23 months of age: Hemoglobin concentration < 105 gram/liter at discharge For children 24-59 months of age: Hemoglobin concentration < 110 gram/liter at discharge	Non-inferiority
Anemia at 3-months post-discharge	For children 6-23 months of age: Hemoglobin concentration < 105 gram/liter at discharge For children 24-59 months of age: Hemoglobin concentration < 110 gram/liter at discharge	Superiority

Sample size

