All analyses will be delineated in detail in the trial Statistical Analysis Plan (SAP) which will be developed and finalized prior to initiation of enrollment. A summary is given here.

The study is powered for separate comparisons between (i) the control group and SMS-RUTF, and (ii) between the control group and S-RUTF. All analyses will be stratified by MAM vs SAM status.

Baseline characteristics will be assessed with descriptive statistics (means and standard deviations for continuous variables, and proportions for categorical variables). Baseline characteristics will be adjusted for in the analyses if it is both (i) associated with treatment outcomes or relapse in published literature and (ii) imbalanced between treatment arms as determined by statistically significant t-test or χ^2 tests with 5% significance level.

For binary outcomes, we will use log-binomial regression to estimate relative risks (RRs) and 95% confidence intervals (CIs) for the RRs, adjusting for any baseline factors as appropriate. Non-inferiority will be declared if the lower bound of a one-sided 95% CI for the RR lies entirely below the non-inferiority margin of a relative 12.5%. For continuous outcomes, we will use linear regression to estimate differences in that outcome between treatment arms, adjusting for any baseline factors as appropriate. For superiority analyses (relapse), we will use a two-sided 95% CI and superiority will be declared if the lower bound of the 95% CI for the relative risk is above 1.0.

Non-inferiority analyses can be spuriously favored by ITT analyses because non-compliance diminishes any treatment effects, thus biasing the effect size toward the null (35). We will therefore repeat all non-inferiority analyses with a per-protocol (PP) population, restricting the analyses to only children who comply with their full treatment course, per caregiver report. The ITT and PP results will be presented side-by-side for non-inferiority analyses; superiority analyses will be analyzed as ITT only.

Adverse event (AE) and serious adverse event (SAE) monitoring and reporting

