## Treatment of missing data

Wherever more than 10% of outcome observations are missing, we will report the number of observations used in the analysis. No imputation of missing data will be done, given the limited number of covariates available to predict missing observations. Every effort will be made to minimize attrition of study participants, thus keeping missing data to a minimum. Default from treatment will be considered a treatment outcome, rather than missing data.

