## Analysis frame

Our primary analysis frame will be intention-to-treat (ITT). ITT groups will be defined by the randomization assignment to which participants are allocated; that is, all participants will be included in the analysis based on the treatment group to which they were randomized.

However, ITT analyses can bias effect sizes toward the null, spuriously demonstrating non-inferiority, because non-compliance diminishes any treatment effects (30). Despite this, ITT is still the recommended approach for non-inferiority trials (31). To mitigate this concern, we will conduct a secondary analysis in which we repeat all analyses with a Complier Average Causal Effects (CACE) approach. CACE analyses adjust for any differences between children who adhere vs do not adhere in characteristics that may influence outcomes, thus mitigating concerns of confounding. CACE analyses are also useful for superiority analyses, as these results can distinguish between the effects of the interventions themselves, and effects of the adherence to the interventions. Both ITT and CACE results will be presented. This is summarized in Table 5.

Adherence will be defined as attendance at all treatment visits. The characteristics to be considered for adjustment and the decision rules to determine whether adjustment will be made will be the same as described in the next section below.

*Table 5. Analysis approaches and sensitivity analyses by type*

Analysis type	Primary analysis	Secondary analysis	Sensitivity analyses
Non-inferiority	ITT	CACE	Exclusion of children who received both study products and standard of care products during treatment course
Superiority	ITT	CACE	Exclusion of children who received both study products and standard of care products during treatment course

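### The per-protocol and CACE repeats cover every outcome, so default, adherence and compliance are analysed within groups those outcomes define; for recovery, the per-protocol repeat can mask a deficit that acts through default

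*Protocol*

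**What the plan says.** Protocol, Statistical analysis: because ITT can spuriously favour non-inferiority, the plan is to "repeat all non-inferiority analyses with a per-protocol (PP) population, restricting the analyses to only children who comply with their full treatment course", with compliance taken from caregiver report. On the use of the two results it says only: "The ITT and PP results will be presented side-by-side for non-inferiority analyses".

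Protocol Table 3 lists these as non-inferiority outcomes and exempts none from the repeat:
- default: "Child is absent for two consecutive visits, declared a defaulter on the second visit"
- adherence: "Caregiver attends the recommended schedule of visits and receive RUTF supply"
- compliance: "The child receives the recommended dose of the RUTF each day"

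The Protocol calls its analysis section a summary and refers to the SAP for detail. The SAP (Analysis frame, Table 5) has no per-protocol analysis. ITT is primary, and a CACE analysis of all outcomes is secondary: "Adherence will be defined as attendance at all treatment visits". Default and adherence remain non-inferiority outcomes in SAP Table 1. Compliance as daily dose does not appear there, although SAP Table 4 keeps a row for compliance described as visit attendance. Under Treatment of missing data: "Default from treatment will be considered a treatment outcome, rather than missing data".

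**The concern.** There are two separate problems.

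First, an outcome that decides who enters the analysis set cannot be compared within that set. The repeats for default, adherence and compliance would print a result known before any data are seen, and a reader could take it as confirmation that the products are equally well tolerated.

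Second, for recovery, the per-protocol repeat exists to guard against an ITT analysis that is too kind to the new product. If a new food leads more families to stop attending, those children count as not recovered under ITT but leave the per-protocol set. The repeat can then look better than ITT for exactly the product it should expose. The route is plausible here: the SAP's Blinding section expects the products to differ in taste and appearance.

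**Working it through.** **1. Circular outcomes (no arithmetic needed).** Under the Protocol, the set is children who comply with the full course by caregiver report. Compliance in that set is 100% in every arm. Default is 0% and adherence 100% if the full course includes the visits, which the Protocol does not spell out. Under the SAP, an adherent child has attended every visit, so has never missed two in a row: default is 0% and adherence 100%. The relative risk is 1 for adherence and compliance, and 0/0 for default. The SAP names no CACE estimator, but no covariate adjustment can create variation in an outcome that is fixed within the group of interest.

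**2. Reproducing the plan's own figure.** Protocol Table 4: control 77%, margin 10 points, one-sided alpha 0.05, 306 analysed per arm, stated power 90.0%. Φ(0.10/√(2·0.77·0.23/306) − 1.645) = Φ(2.939 − 1.645) = 90.2%. The figure reproduces.

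**3. Inputs for recovery.**
- 360 enrolled per arm and severity stratum; control recovery 77% (Protocol, Sample size).
- Control default 8.5% (SAP Table 4, SAM).
- Margin of a relative 12.5%, read as requiring the one-sided 95% lower bound of the RR to exceed 0.875.
- Assumed: true deficit of 10 points (67% against 77%); defaulters count as not recovered under ITT; per-protocol removes defaulters only.
- Assumed: f, the share of excess failures that occur as default. The documents do not give it, so the range 0 to 1 is shown.

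**4. Formula.** Pass probability = Φ((ln RR − ln 0.875)/SE − 1.645), with SE² = (1−p_C)/(n_C·p_C) + (1−p_T)/(n_T·p_T). For per-protocol, p_C = 0.77/(1−0.085), p_T = 0.67/(1−0.085−0.10f), and each n is 360 times the same denominator.

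**5. ITT.** RR = 0.67/0.77 = 0.870, SE = 0.0469. Φ((−0.1391 + 0.1335)/0.0469 − 1.645) = 3.9%, for every f.

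**6. Per-protocol.**

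| f | Default, new arm | Recovery, control vs new | RR | Pass, 360 per arm | Pass, 306 per arm |
|---|---|---|---|---|---|
| 0 | 8.5% | 84.2% vs 73.2% | 0.870 | 4% | 4% |
| 0.25 | 11.0% | 84.2% vs 75.3% | 0.895 | 14% | 13% |
| 0.5 | 13.5% | 84.2% vs 77.5% | 0.920 | 37% | 33% |
| 0.75 | 16.0% | 84.2% vs 79.8% | 0.948 | 69% | 62% |
| 1 | 18.5% | 84.2% vs 82.2% | 0.977 | 92% | 88% |

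**7. Sensitivity to the recovery rate.** In SAP Table 4, the 8.5% default rate comes from the source that reports 55.4% SAM recovery. With 55.4% against 45.4%, ITT passes 0.6%. At f = 1, per-protocol compares 60.5% with 55.7% (RR 0.920) and passes 18%.

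**8. How much of failure is default.** From SAP Table 4, SAM: 8.5/(8.5 + 20.1 + 12.5) = 21% of listed failures (default, transfer, non-response). MAM: 6.8/(6.8 + 5.8 + 28) = 17%. These are shares of total failure, not of the excess, so they do not fix f.

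**The case against.** The strongest reply has four parts.

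- **The SAP supersedes the Protocol's per-protocol analysis.** True, and CACE as named is not a restriction to attenders. The percentages above therefore describe the Protocol's analysis and cannot be carried over to CACE. The circularity for default and adherence does carry over, because the SAP also repeats everything and defines adherence by attendance.
- **Per-protocol cannot pass an inferior product.** A reader might infer from the 92% that the trial would declare an inferior product non-inferior at that rate. The documents do not support this. ITT is primary in the SAP, and no rule lets the per-protocol result decide alone. If both must pass, the error cannot exceed that of ITT.
- **The harm would show elsewhere.** Also largely right. At f = 1, default is 18.5% against 8.5% (RR 2.18). Against the 45% relative margin for SAM in SAP Table 4, with SE 0.205, the ITT chance of passing is Φ((ln 1.45 − ln 2.18)/0.205 − 1.645), about 0.015%.
- **Failures are not all removed.** A reader might take the per-protocol set to be children who completed treatment successfully. The text says comply, so a complying non-responder stays in as a failure. Whether a transferred child counts as compliant is not stated.

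What remains is that the Protocol adds the repeat as protection and shows it beside ITT without saying how to read a disagreement.

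**Conclusion.** The concern holds in limited form. The circularity follows from the wording of both documents: for compliance in the Protocol with certainty, and for default and adherence wherever complying includes attending, as in the SAP.

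For recovery, the per-protocol repeat is an unreliable safeguard. Under a 10-point deficit its pass rate runs from 4%, the same as ITT, to 92%, depending entirely on an assumed share that the documents do not give. The high end also depends on pairing 77% recovery with an 8.5% default rate; with the 55.4% recovery from the same source it falls to 18%. Nothing here shows that the primary conclusion would be wrong, since ITT is primary and default is tested by ITT. The Protocol and SAP also disagree on which repeat is to be done and on how compliance is measured.

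**What to change.** - In the Protocol's Statistical analysis and the SAP's Analysis frame, replace the blanket repeat with a named list of outcomes. State that default, adherence and compliance are analysed by ITT only.
- Reconcile the two documents: per-protocol by caregiver-reported compliance, or CACE by attendance. Say whether a transferred child counts as compliant.
- State that the per-protocol or CACE result for recovery cannot establish non-inferiority without the ITT result, and present it beside default by arm.

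Redefining the per-protocol set to keep defaulters and transfers as failures is not needed for this point. It would pull the analysis back toward ITT, which is a debatable trade.

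The cost is wording in two sections and no new data. The downside is fewer side-by-side results.

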## List of acronyms

ABC-I	Activity-based costing–ingredients
AE	Adverse event
ALR	Additive log-ratio
ANCOM-BC2	Analysis of Composition of Microbiomes with Bias Correction 2
ANOVA	Analysis of variance
CACE	Complier Average Causal effects
CI	Confidence interval
CLR	Centered log-ratio
CMAM	Community Management of Acute Malnutrition
CONSORT	Consolidated Standards of Reporting Trials
CSPS	Centre de Santé et Promotion Sociale
DALY	Disability-adjusted life year
DSMB	Data Safety and Monitoring Board
ELISA	Enzyme-linked immunosorbent assay
GDP	Gross domestic product
HAZ	Height-for-age Z-score
ICC	Intra-class correlation coefficient
IFPRI	International Food Policy Research Institute
IRB	Institutional Review Board
IRSS	Institut de Recherche en Sciences de la Santé
IQR	Interquartile range
ITT	Intention-to-treat
LAZ	Length-for-age Z-score
LMM	Linear mixed model
LOS	Length of stay
MaAsLin2	Multivariate Association with Linear Models 2
MAM	Moderate Acute Malnutrition
MUAC	Mid-upper arm circumference
PERMANOVA	Permutational multivariate analysis of variance
RR	Relative risk
RUSF	Ready-to-use supplementary food
RUTF	Ready-to-use therapeutic food
SAE	Severe adverse event
SAM	Severe Acute Malnutrition
SAP	Statistical analysis plan
SD	Standard deviation
SMS-RUTF	Soy–maize–sorghum–based ready-to-use therapeutic food
SOP	Standard operating procedure
S-RUTF	Soy-based ready-to-use therapeutic food
UniFrac	Unique fraction distance metric
WAZ	Weight-for-age Z-score
WHO	World Health Organization
WHZ	Weight-for-height Z-score
WLZ	Weight-for-length Z-score

## Background

Acute malnutrition is the most life-threatening form of undernutrition. Moderate and severe acute malnutrition (MAM, SAM) are effectively treated with ready-to-use therapeutic foods (RUTFs) but there is a need to lower the cost of treatment and improve treatment regimens to reduce risk of relapse MAM/SAM episodes following recovery. The currently used standard formulation of RUTF contains peanuts and dairy, which pose problems due to their high cost, the need to import ingredients to the Global South (in the case of dairy), and risk of aflatoxin (in the case of peanuts). Before alternative formulations of RUTF can be recommended, however, there is the need for data on the non-inferiority of these formulations compared to the most commonly used milk- and peanut based RUTF on recovery rates and to what extent recovery is sustainable. Sustainable recovery implies a lower rate of post-treatment relapse. In this study we evaluate two novel RUTF formulations, one that is peanut and milk-free based on soy, maize and sorghum (SMS-RUTF) and one with reduced milk based on soy (S-RUTF).

## Hypotheses and Objectives

### Main trial

1. To assess the non-inferiority of novel soy-maize-sorghum (SMS-) RUTF and soy-based (S-) RUTF on treatment recovery to standard RUTF  
Hypothesis: MAM and SAM children who received SMS-RUTF or S-RUTF during treatment will have non-inferior recovery rates, compared to those who received standard RUTF.
2. To assess the superiority of SMS-RUTF and S- RUTF on post-recovery relapse compared to standard RUTF  
Hypothesis: MAM and SAM children who received SMS-RUTF or S-RUTF during treatment will have lower relapse rates compared to children who received standard RUTF.

### Sub-study 1: Acceptability

1. To assess the acceptability of S-RUTF and SMS-RUTF in MAM children  
Hypothesis: SMS-RUTF and S-RUTF will each have similar acceptability compared to standard RUTF
2. To assess the sensory adaptation to the products  
Hypothesis: The children adapt to the product with increased intake over time.

### Sub-study 2: Microbiome and gut health

1. To evaluate the association between intestinal, inflammation microbiome composition and enteropathogen burden (collectively referred to as “gut health” in this document) and relapse rates in children with SAM treated with SMS-RUTF, S-RUTF, or standard RUTF.  
Hypothesis: Improved gut health will be associated with lower relapse rates in all treatment groups  
Improved gut health will be associated with lower relapse rates in children treated with SMS-RUTF and S-RUTF compared to those receiving standard RUTF
2. To assess the impact of SMS-RUTF and S-RUTF gut health, relative to standard RUTF, in children with SAM.

Hypothesis: SMS-RUTF and S-RUTF will have a more favorable impact on gut health compared to standard RUTF in children with SAM.

### Sub-study 3: Costing

1. To estimate the cost-efficiency and cost-effectiveness SMS-RUTF, S-RUTF, and standard RUTF  
Hypothesis: Not applicable as no statistical hypothesis testing will be done.

## Study methods

### Study setting

Burkina Faso is a land-locked country in West Africa with a high burden of wasting, with national prevalences estimated at 9.7% of children under age 5 (1). Burkina Faso has seen deteriorating humanitarian conditions since 2020, with numbers of internally displaced persons exceeding 2 million due to security incidents, and increasing populations of refugees primarily from Mali. In addition to the intensifying displacement, the food security situation has deteriorated significantly and 630,000 children in Burkina Faso are projected to be acutely malnourished in 2023. This study will be conducted in 30 health centers (Centres de Santé et Promotion Sociale [CSPSs]) in the Hauts-Basin region of Burkina Faso. CSPSs with the highest caseloads in the Dande, Dafra, Karangasso, and Houde health districts will be selected.

### Study design

#### Main trial

This will be a facility-based, triple blinded individually randomized controlled trial with three arms, including two interventions and one control arm, with a 1:1:1 allocation ratio. Children will be enrolled upon initiation of MAM or SAM treatment and followed monthly for 3 months post-discharge from treatment.

#### Sub-study 1: Acceptability

In a sub-set of facilities, we will conduct a 3x3 full Latin square crossover design to evaluate acceptability of the two products to address objective 1 (acceptability of S-RUTF and SMS-RUTF) and assess the adaptation to the products to address objective 2 (sensory adaptation). The 3x3 full Latin square crossover design will involve measurements of the RUSFs' observed intakes at four time points — baseline (day 1), day 8 (product switching), day 15 (product switching), and day 22.

#### Sub-study 2: Microbiome and gut health

In a subset of facilities, fecal samples will be collected at baseline (admission), discharge, and 3 months post-discharge or upon relapse within 3 months after discharge from treatment.

#### Sub-study 3: Costing

We will employ an activity-based costing-ingredients (ABC-I) approach to collect and analyze data on costs incurred in each treatment arm. This approach involves documenting all costs and allocating them to the activity in which they were incurred. Both societal and health system perspectives will be used. The health system perspective includes only costs to the health system, whereas the societal perspective includes health system costs as well as expenses and opportunity costs to caregivers (2,3). This will include costs and opportunity costs to caregivers.

